Immortalized mouse proximal tubule cells consists of cells originating from the early segment of the mouse proximal tubule. To demonstrate the effects of high glucose on AGT expression in this cell line, mPTCs were seeded on 6-well plates at a density of 5.0×105 cells per well. Before treatment in high glucose, the cells were rinsed with PBS and treated in 1.5 mL serum-free DMEM (5 mM glucose) for 8 hours. For high glucose treatment, serum-free Dulbecco Modified Eagle's Medium (DMEM) was supplemented with glucose to a final concentration of 5 mM (control), 15 mM, or 25 mM (n = 4). The cells were incubated at 37 °C for 24 hours. After treatment, cell lysates were prepared. AGT protein was detected via western blot analysis. The results of this experiment showed that our mPTC cell line exhibits a significant increase in AGT expression under high glucose conditions (15 mM and 25 mM glucose) compared to normal glucose (5 mM glucose). To test the effects of high glucose on AGT mRNA, cells were cultured as previously described in serum-free DMEM with 5 mM or 25 mM glucose (n = 3) and incubated at 37 °C.

After 24 hours, AGT mRNA was quantified via qRT-PCR. AGT mRNA relative to GAPDH mRNA was found to be significantly higher after treatment in 25 mM glucose.

The results of these preliminary experiments demonstrate that our mPTC line exhibits very low expression of AGT under normal glucose conditions (5 mM).

The impact of treatment with an SGLT2 inhibitor on intra –renal AGT production is unknown. Additionally, it is unclear what the impact of having significant glycosuria will have on AGT production. Finally, it is important to determine if there are differential effects on AGT production between SGLT2 inhibition and other methods of improving glycemic control, such as Sulfonylurea therapy

Proposed Studies

We propose to conduct a single-center randomized, double blind, cross over study of the effect of Dapagliflozin over 6 weeks, followed by placebo over 6 weeks on the other treatment allocation (those getting placebo first will cross over to Dapagliflozin and vice versa). Treatment will be stratified according to the underlying presence or absence of hypertension.

- 1. Type 2 diabetes with hypertension and on RAAS blocking drugs with stable blood pressure on therapy for at least 30 days; n= 20
- 2. Type 2 diabetes without hypertension and not on RAAS blocking drugs n=10

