If we are unable to recruit 10 patients without hypertension we will increase the number with hypertension for a total of 30. Stratification by hypertension status will remain and is important in understanding the effect of SGLT2 inhibition in patients not on BP lowering drugs

In addition a Sulfonlyurea (SU) arm will also be included -10 patients who are on metformin and other background therapy (with the exclusion of SGLT-2 inhibitor and sulfonylurea) will be recruited. This will be an open-labeled arm. Patients will assessed at baseline. They will then receive usual care for 6 weeks. At the end of 6 weeks, patients will then undergo another assessment before being provided SU for 6 weeks. At the end of 6 weeks, patients will undergo assessment again. The aim is to determine whether any effects seen with Dapagliflozin are specific to that drug or related simply to improved glycemic control.

Inclusion criteria;

As per the current approved indications for Dapagliflozin. In addition;

- 1. Type 2 diabetes with hypertension (history of hypertension in clinical records and on medication for management of hypertension) and on RAAS blocking drugs; or
- 2. Type 2 diabetes without hypertension and not on RAAS blocking drugs
- 3. Hemoglobin A1c between 7% 10% inclusive
- 4. Background therapy for diabetes to include maximally tolerated dose of metformin.
- 5. For the dapagliflozin/placebo arm, in addition to metformin, sulfonylureas and/or insulin is allowed
- 6. Estimated glomerular filtration rate (eGFR) > = 60 ml/min
- 7. Between the ages of 18 -75
- 8. Capacity to understand and sign the informed consent.

Exclusion criteria:

- 1. Current use of Dapagliflozin or any SGLT2 inhibitor
- 2. History of intolerability to Dapagliflozin
- 3. Patients with current and past history of bladder cancer
- 4. Patients with unexplainable baseline hematuria
- 5. All current contraindications of Dapagliflozin as per the label
- 6. Severe hepatic insufficiency and/or significant abnormal liver function defined as aspartate aminotransferase (AST) >3x upper limit of normal (ULN) and/or alanine aminotransferase (ALT) >3x ULN
- 7. Total bilirubin >2.0 mg/dL (34.2 μ mol/L)
- 8. Estimated glomerular filtration rate (eGFR): <60 mL/min (calculated by Cockcroft-Gault formula)
- 9. Recent Cardiovascular Events in a patient:
- 10. Acute Coronary Syndrome (ACS) within 2 months prior to enrolment

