- 11. Hospitalization for unstable angina or acute myocardial infarction within 2 months prior to enrolment
- 12. Acute Stroke or TIA within two months prior to enrolment
- 13. Less than two months post coronary artery revascularization
- 14. Congestive heart failure defined as New York Heart Association (NYHA) class IV, unstable or acute congestive heart failure. Note: eligible patients with congestive heart failure, especially those who are on diuretic therapy, should have careful monitoring of their volume status throughout the study.
- 15. Pregnant or breastfeeding patients
- 16. Patients who, in the judgment of the investigator, may be at risk for dehydration
- 17. Blood pressure: At enrolment: Systolic BP ≥165 mmHg and/or diastolic BP ≥110 mmHg
 a. At randomization: Systolic BP ≥160 mmHg and/or diastolic BP ≥100 mmHg
- 18. For patients in the dapagliflozin/placebo arm, use of SGLT-2 inhibitor class of drugs is an exclusion.
 Patients may continue the background therapy.
 - a. For patients that will be included in the sulfonylurea/placebo arm use of SLGT-2 inhibitor and sulfonylurea class of drugs in an exclusion. Patients can continue the rest of the background therapy.

Methods:

Once the subjects have been provided with the informed consent procedure and have signed the approved consent form and HIPAA form, the screening procedure will commence. Screening will include a completed medical history and list of current medications to determine eligibility for participation in this study. Details of the procedures are listed in the visit schedule section (see below).

Blinding and unblinding:

The research study participants will be blinded throughout the study in the dapagliflozin-placebo arm. Unblinding will be done only in case of emergency for patient safety. In this case, unblinding will be done by the sponsor or the research site as the randomization code will be with the sponsor.

The SU arm will be open label arm.

Storage of investigational product:

All study drugs should be kept in a secure place and under appropriate storage conditions. The Investigational Product label on the bottle specifies the appropriate storage

Accountability:

Storage of IP will be handled by the Investigational Pharmacist, who will maintain both accountability for the IP as well as maintenance of the IP, according to the manufacturer's requirements and recommendations for product safety.

Labeling of drug:

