This is a pilot study. Data from this study can be used to derive the sample size for an adequately powered study. Exploratory data analysis: All data will be cleaned and logically checked.

Exploratory analysis will be conducted to examine the distributions of each variable by means of plots (bar charts, box plots, and normal probability plots) and goodness-of-fit test statistics. Means and percentages of baseline variables will be compared between the groups. Possible outliers will be detected. Data transformation will be used to normalize the distribution of continuous variables and to improve linearity in the linear regression analyses if needed.

Comparisons of continuous variables between groups will be performed using t-tests. Chi-square tests will be employed for comparisons between categorical data. Linear regression models will be fit to examine the association between a continuous dependent variables and possible independent co-variables. Data analyses will be performed using SAS version 9 (SAS Institute Inc., SAS/STAT User's Guide, Version 9. Cary, NC: SAS Institute Inc. 2007).

Patient Safety:

A copy of the MedWatch/AdEERs report will be faxed to AstraZeneca at the time the event is reported to the FDA. It will be the responsibility of the investigator to compile all necessary information and ensure that the FDA receives a report according to the FDA reporting requirement timelines and to ensure that these reports are also submitted to AstraZeneca at the same time. When reporting to AstraZeneca, a cover page will accompany the MedWatch/AdEERs form indicating the following:

- Investigator Sponsored Study (ISS)
- The investigator IND number assigned by the FDA
- The investigator's name and address
- The trial name/title and AstraZeneca ISS reference number

The collection of AEs should start after the signing of the informed consent. Investigative site will also indicate, either in the SAE report or the cover page, the causality of events in relation to all study medications and if the SAE is related to disease progression, as determined by the principal investigator. The site research personnel will send SAE report and accompanying cover page by way to AstraZeneca: [contact] or fax number is [contact].

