Fasting glucose, blood and urine samples	Dapagliflozin/placebo - At the beginning of test period 1 - Before the end of test period 1 - At the beginning of test period 2 - At the beginning of test period 2 - At the beginning of test period 2 Sulfonylurea arm - Before the usual care arm visit (in test period 1)		
	 At the end of test period 1 At the end of test period 2 (at the end of the study) 		
EndoPAT Procedure	 Dapagliflozin/placebo arm only Before randomization visit (in test period 1) At the end of test period 1 At the beginning of test period 2 At the end of test period 2 		

The **primary end point** will be reduction in urine AGT comparing the AGT before and after treatment using a paired ANOVA Test.

Exploratory endpoints will be:

- 1. Examine the relationship between change in plasma K and change in urine AGT
- 2. Examine the relationship between change in BP and change in endothelial function/vascular compliance using the EndoPAT procedure.

Depending on results of this pilot study we will plan further definitive studies of the effect of SGLT2 inhibition on urine AGT, in a study with appropriate statistical power.

Forecasted key milestones dependent on IRB/IEC approval and contracting

1.	Research Agreement executed	Feb 28, 2016
2.	Projected IRB/IEC approval	Feb 28, 2016

- 3. First Subject In Apr 29, 2016
- 4. Last Subject In (100% enrollment) Apr 30, 2017
- 5. Last Subject Last Visit (Treatment end) Jun 30, 2017
- 6. Publication Jan 30, 2018

References

- 1. McFarlane SI. In: Izzo JL, Black HR, eds. *Hypertension primer: The essentials of high blood pressure*. Lippincott Williams & Wilkins; 2003:488.
- 2. National diabetes fact sheet. 2011

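### The sulfonylurea arm is meant to separate a drug-specific AGT effect from a glycemic one, but no adjusted dapagliflozin-versus-sulfonylurea estimate is specified for that aim

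*Combined protocol and SAP*

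**What the plan says.** - **Aim.** Preliminary Studies states that "it is important to determine if there are differential effects on AGT production between SGLT2 inhibition and other methods of improving glycemic control", with SU therapy as the example. Proposed Studies gives the SU arm its purpose: "The aim is to determine whether any effects seen with Dapagliflozin are specific to that drug or related simply to improved glycemic control".
- **SU arm design.** Ten patients, open label. They are assessed at baseline and then have six weeks of usual care. "At the end of 6 weeks, patients will then undergo another assessment before being provided SU for 6 weeks". Randomisation (Visit Schedule, visit 3) covers only dapagliflozin or placebo.
- **Background therapy.** Inclusion criterion 5: "For the dapagliflozin/placebo arm, in addition to metformin, sulfonylureas and/or insulin is allowed". Exclusion criterion 18a: "For patients that will be included in the sulfonylurea/placebo arm use of SLGT-2 inhibitor and sulfonylurea class of drugs in an exclusion".
- **Analysis.** The primary end point, stated after the timing table, is "reduction in urine AGT comparing the AGT before and after treatment using a paired ANOVA Test". Neither exploratory end point involves SU. The statistical section adds "Comparisons of continuous variables between groups will be performed using t-tests" and "Linear regression models will be fit to examine the association between a continuous dependent variables and possible independent co-variables". It names no arms, AGT change score, control period or covariates.
- **Glucose.** Fasting plasma glucose is measured in both arms (Measurements, item 4), but no analysis relates it to AGT. SU titration is left to the principal investigator (Dose and treatment regimens).

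**The concern.** A paired test within each arm answers whether AGT changed in that arm. It does not answer whether the change on dapagliflozin differs from the change on SU, and the aim depends on that difference. The reader is left with two routes.

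1. Compare the two within-arm results informally. With 30 patients on one side and 10 on the other, the larger group will often reach significance alone, even if both drugs do the same thing.
2. Apply the general t-test to the two groups. This is a direct comparison, but the groups differ by design in background SU, in order of treatment and in blinding. They may also differ in hypertension/RAAS mix and in how far glucose falls. Shared eligibility (HbA1c 7–10%, metformin, eGFR) limits these differences without removing them.

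By either route, an effect of glucose lowering could be reported as specific to dapagliflozin.

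**Working it through.** The documents give no SD, alpha, power or effect size, so there is no stated figure to reproduce beyond 20 + 10 = 30 in the crossover. Everything below is illustrative: two-sided 0.05, no dropout, and effects in units of the SD of one within-patient change, assumed equal in both arms.

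**1. Separate within-arm tests, equal true effects.** P(significant at n = 30, not at n = 10) = p30 × (1 − p10), with each power from the one-sample t-test and the arms independent.

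| True effect (SD) | p30 | p10 | p30 × (1 − p10) |
|---|---|---|---|
| 0.2 | 0.185 | 0.088 | 17% |
| 0.4 | 0.563 | 0.205 | 45% |
| 0.6 | 0.888 | 0.396 | 54% |
| 0.8 | 0.988 | 0.616 | 38% |
| 1.0 | 1.000 | 0.803 | 20% |
| 1.2 | 1.000 | 0.920 | 8% |

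**2. Plain two-sample t-test, 30 v 10, no drug-specific effect.** Two-sided rejection is 5% if the arms are comparable. It is 8%, 19% and 36% if imbalance shifts the change by an assumed 0.2, 0.4 and 0.6 SD.

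**3. Precision of a direct contrast.** Take end of treatment minus end of control period within each patient. The 95% half-width is t(0.975, n1 + 8) × √(1/n1 + 1/10), where n1 is the number of crossover patients:
- n1 = 30: 2.024 × √(1/30 + 1/10) = 2.024 × 0.365 = 0.74 SD.
- n1 = 20, 15 or 10, if only that many are off background SU: 0.79, 0.85 or 0.94 SD.

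The difference detectable with 80% power at 30 v 10 is 1.05 SD. Power at 0.5, 0.8 and 1.0 SD is 27%, 57% and 76%.

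**4. Drift in the fixed-order arm.** SU always follows usual care, so a steady drift of d per six weeks biases the contrast in step 3 by d. In a simulation with no drug effect (40,000 runs, 15 patients per sequence, three-week washout assumed), drift of 0.2 or 0.4 SD raised its two-sided rejection to 8% or 16%.

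The alternative is change over the drug period minus change over the control period. Its SU component is (week 12 − week 6) − (week 6 − week 0), so linear drift cancels. A one-time fall in the first period of 0.2, 0.4 or 0.6 SD, however, biases it by the full amount in dapagliflozin's favour. Its half-width is 2.024 × √(2/30 + 3/10) = 1.23 SD. It can serve as a check on drift but is too imprecise to be the main estimate.

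**The case against.** The strongest reply is that the analysis is under-specified rather than absent. The statistical section names between-group tests and regression with covariates, the SU arm is an obvious group, and the regression could carry an arm term. The study calls itself a pilot, and the SU comparison is neither the primary nor a listed exploratory end point. All of that is true. It excuses low power and lowers the stakes. It does not supply the contrast, and the only group comparison actually named is unadjusted.

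Four stronger readings are tempting and are not supported:

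- *That the investigators will infer specificity from one arm being significant and the other not.* No passage says so. The 17–54% shows what that reading would cost if it were used.
- *That a specificity claim will pass into the definitive study.* The protocol plans further work on SGLT2 inhibition and urine AGT, without mentioning specificity.
- *That the SU arm's control is undefined.* Proposed Studies, the open-label statements and the timing table all describe usual care followed by SU, and Appendix A lists only dapagliflozin and its matching placebo. The sulfonylurea/placebo wording (exclusion 18a; Measurements, item 1) and the reference to titrating a placebo (Dose and treatment regimens) are an inconsistency to reconcile.
- *That specificity should be claimed only if both forms in step 4 agree.* In simulation this cuts the chance of a result favouring dapagliflozin from 54/73/87% (main contrast alone) to 22/34/46% at true specific effects of 0.8/1.0/1.2 SD. It also leaves the bias from unequal glucose lowering in both estimates.

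Non-randomisation, fixed order and discretionary titration are openly stated design features that analysis wording cannot repair.

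**Conclusion.** The point holds in a limited form. The documents set a between-arm AGT question and tie no between-arm analysis to it. The general t-test that could be applied is open to confounding by background SU, hypertension/RAAS status and treatment order. An adjusted contrast, each drug net of its own control period, is a better method and uses data already scheduled. The point concerns a stated secondary purpose of the study, not the randomised dapagliflozin-versus-placebo comparison. The error rates rest on assumed effects, imbalances and drifts in SD units, because the documents give no AGT variability. Even the better contrast cannot remove unequal glucose lowering or drift in the SU arm. At about ±0.74 SD it is likely to be inconclusive unless the drug-specific effect is large.

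**What to change.** For this aim, pre-specify:

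1. **One exploratory, non-randomised dapagliflozin-versus-SU estimate with a 95% CI.** The outcome is log urinary AGT/creatinine, as end of treatment minus end of control period within each patient. Include a period term in the crossover, and adjust for hypertension/RAAS stratum and study-entry (visit 2) log AGT. The regression already named can carry this.
2. **Sensitivity analyses.** (a) Restrict the crossover to patients not on background SU. (b) Report change from period start on drug minus the same on control, as a check on drift only and with no agreement rule. Do not adjust (b) for study-entry AGT, which it already contains.
3. **A supportive analysis** adjusting for change in fasting glucose, labelled as such because that change occurs after treatment starts.
4. **Stated limits.** Specificity will not be inferred from one arm being significant and the other not. The comparison cannot remove unequal glucose lowering or drift in the fixed-order SU arm.
5. **Reconciled arm description.** Bring exclusion 18a, Dose and treatment regimens, and Measurements item 1 into line with the usual-care-then-SU account in Proposed Studies, since these passages define the control period.

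The cost is plan wording and a corrected arm description. Urine and fasting glucose samples are already scheduled in both arms, and current medications are listed at screening. The downside is a wide interval and a less definite conclusion.

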Rationale: Clinical trials of two SGLT2 inhibitors, canagliflozin and dapagliflozin, have reported drops in systolic blood pressure of ~5 mmHg^{3, 4}. Inappropriate activation of intrarenal renin-angiotensin system (RAS) is a major contributor to the increased arterial pressure and tissue injury including diabetic nephropathy. A key factor in the intrarenal RAS activation is stimulation of intrarenal angiotensinogen (AGT) which is the precursor of angiotensin peptides⁵. In animal models of type1 and type 2 diabetes mellitus, hyperglycemia is accompanied by elevated intrarenal AGT and urinary AGT levels⁶⁻⁸. Furthermore, direct treatment of rat renal proximal tubular cells (PTC) with high glucose results in stimulation of AGT production⁹. These findings suggest that hyperglycemia augments intrarenal AGT levels in diabetes mellitus leading to the development of high blood pressure and diabetic nephropathy.

By inhibiting glucose reabsorption in the proximal tubule, SGLT2 inhibition has the potential to block the AGT elevating effect of hyperglycemia. We therefore submit the following:

Hypothesis 1: SGLT2 inhibition attenuates renal AGT elevation by hyperglycemia leading to decreased blood pressure, renoprotection and cardio protection in diabetes mellitus. This effect can be elucidated by simultaneously measuring urine AGT and 24 hour ambulatory blood pressure (ABPM)

We will test this hypothesis in a pilot study by:

Aim 1. Exploring the effect of SGLT2 inhibition on intra-renal AGT production in subjects with diabetes mellitus, who are known to have augmentation of intra – renal AGT.

This will be a cross-over pilot study to elucidate whether this mechanism underlies the decrease in BP, as well as the rise in K, in humans with diabetes.

Background

Specific Aim: Explore the effect of SGLT2 inhibition on intra-renal AGT production in subjects with diabetes, who are known to have augmentation of intra – renal AGT.

Rationale: We have recently demonstrated that urinary AGT is increased in patients with diabetes, including patients with diabetes without microalbuminuria and hypertension (not yet published). The increase is greatest in those with established

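### No period of unchanged glucose-lowering doses is required before baseline, so AGT drift from a recent change can enter the before-versus-after primary result (minor)

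*Combined protocol and SAP*

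**What the plan says.** The Inclusion criteria name the background drugs but give no time on dose. Item 4: "Background therapy for diabetes to include maximally tolerated dose of metformin". Item 5, for the dapagliflozin/placebo arm: "in addition to metformin, sulfonylureas and/or insulin is allowed". The sulfonylurea arm is described under Proposed Studies: "10 patients who are on metformin and other background therapy (with the exclusion of SGLT-2 inhibitor and sulfonylurea) will be recruited". Exclusion 18 only lets background therapy continue.

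The one stability condition in the plan concerns blood pressure. It stands in the stratum list under Proposed Studies: "Type 2 diabetes with hypertension and on RAAS blocking drugs with stable blood pressure on therapy for at least 30 days; n= 20". The other stratum, "Type 2 diabetes without hypertension and not on RAAS blocking drugs n=10", carries no such condition, and inclusion item 1 does not repeat it.

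The Visit Schedule describes no run-in. Laboratory results up to ninety days old may establish eligibility, randomization follows within four weeks, and screening and baseline are combined when results are already to hand.

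The opening Rationale concludes from animal and cell work that "hyperglycemia augments intrarenal AGT levels in diabetes mellitus". The primary end point, under Measurements, is "reduction in urine AGT comparing the AGT before and after treatment using a paired ANOVA Test". It names neither a comparison with placebo nor a period term.

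**The concern.** A patient whose metformin reached its maximum, or whose insulin was started, a week before Visit 2 is eligible. The HbA1c that qualified this patient may pre-date the change. On the protocol's own theory, glucose that is still moving at baseline would carry AGT with it. A recent intensification would push AGT down and a recent reduction would push it up, whatever study treatment follows. A before-versus-after contrast cannot tell that movement from a drug effect.

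The sulfonylurea arm exists to show whether any dapagliflozin effect is specific to the drug or reflects better glycaemic control. It is open label, has 10 patients, and always runs usual care first. Drift there is not balanced by randomization and bears directly on that question.

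This is about movement already under way at entry. Changes to background drugs during the trial, which the plan leaves to the principal investigator, are a separate matter.

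**Working it through.** There is no plan figure to reproduce: the protocol gives no AGT standard deviation, effect size, alpha or power. What follows is an illustration on assumptions.

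**From the documents:** six-week periods; washout 14-28 days (21 days used); a new baseline at Visit 8; 20 + 10 = 30 crossover patients; 10 sulfonylurea patients with six weeks of usual care, then six weeks of sulfonylurea.

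**Assumed:** a fraction f = 10-30% of patients had a recent change; each drifts to a ratio d = 0.8 to 0.7 over the first six weeks; the drift decays exponentially with time constant τ = 3 to 6 weeks; the two sequences are of equal size; the before value is the one at the start of the period concerned.

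**1. Drift falling wholly in the first six weeks.** Shift = exp(f × ln d) - 1.
- f = 0.1, d = 0.8: -2.2%
- f = 0.2, d = 0.7: -6.9%
- f = 0.3, d = 0.7: -10.1%

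**2. Allowing for the crossover.** Period 2 starts 6 + 3 = 9 weeks after baseline, so its drift is exp(-9/τ) of that in period 1: 0.050 at τ = 3 and 0.223 at τ = 6. With half the patients on dapagliflozin in each period, the average factor is (1 + 0.050)/2 = 0.525 to (1 + 0.223)/2 = 0.612.
- Smallest: exp(0.525 × 0.1 × ln 0.8) - 1 = -1.2%
- Largest: exp(0.612 × 0.3 × ln 0.7) - 1 = -6.3%

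**3. What that does to a before/after test.** With no drug effect, a mean fall of 0.1, 0.2 or 0.3 SD of the AGT change makes a two-sided 5% paired test at n = 30 reject in 8.3%, 18.5% or 35.5% of trials. With an assumed within-patient log-SD of 0.5, the SD of a change is √(2 × 0.5²) = 0.707. The largest shift in step 2 is 0.0654 on the log scale, or 0.0654/0.707 = 0.09 SD. That is just under the 8.3% case.

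**4. Dapagliflozin versus placebo, adjusted for period.** A crossover of 15 + 15 patients was simulated (20,000 runs per setting) with heavier drift: 25-50% of patients drifting by 0.5-1 SD, τ = 3 weeks. The before/after test on dapagliflozin rejected in 6.0-20.1% of runs; the period-adjusted contrast rejected in 4.6-5.1%. The added variance is f(1-f)(ln d)². At f = 0.2 and d = 0.7 this is 0.16 × 0.127 = 0.020, against 2 × 0.5² = 0.5, or about 4%.

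**5. Sulfonylurea arm, one patient in 10 with d = 0.7.**
- Usual-care period: exp(0.1 × ln 0.7) - 1 = -3.5%.
- Sulfonylurea period: its drift is exp(-6/τ) of that, 0.135 to 0.368. The shift is exp(0.135 × 0.1 × ln 0.7) - 1 = -0.5% to exp(0.368 × 0.1 × ln 0.7) - 1 = -1.3%.
- Sulfonylurea change relative to usual-care change: exp(-(1 - 0.368) × 0.1 × ln 0.7) - 1 = +2.3% to exp(-(1 - 0.135) × 0.1 × ln 0.7) - 1 = +3.1%. Sulfonylurea looks weaker by that amount.

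Drift upward after a dose reduction reverses every sign.

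**The case against.** The strongest reply is that the design already deals with most of this. Order is randomized, patients on dapagliflozin second have a new baseline at Visit 8, and a comparison with placebo with a period term removes the drift in expectation. On that view the real defect is the loosely worded primary contrast. This largely stands. A reader might infer that the randomized comparison is biased, or that the full -2% to -10% applies to the dapagliflozin result; neither follows from the documents. But the plan does not state the placebo contrast for the primary end point. It states before versus after, and there the drift counts.

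A reader might also infer that the fixed order inflates the sulfonylurea effect by the full 3.5%. It does not, because six weeks of usual care come before the pre-sulfonylurea assessment and absorb most early drift. What remains is distortion in the opposite direction when the two periods are compared.

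The 30-day condition is easily over-read as a rule on antihypertensive doses. It is "stable blood pressure on therapy for at least 30 days", and only for the hypertensive stratum. It shows that the sponsor considered stability for blood pressure; it is not a contradiction in the plan.

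That glucose moves AGT in these patients is the protocol's premise, resting largely on animal and cell work, and is close to what the trial tests. The drift is therefore conditional on that premise.

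There are partial safeguards. A maximally tolerated metformin dose suggests that titration is over, medications are listed at screening, patients log blood sugars, and fasting glucose is measured at the start and end of periods. These may reveal drift. They do not prevent it, and the metformin wording says nothing about insulin or other drugs.

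**Conclusion.** The gap is real and minor. Nothing in the plan keeps a recent change in background glucose-lowering treatment out of either arm, and the primary contrast as worded would count the resulting AGT drift. On the stated assumptions the average before/after shift on dapagliflozin is about -1% to -6%, with the opposite sign if doses were recently reduced. The period-adjusted contrast with placebo is unbiased and gains only a little noise. In the sulfonylurea arm, one drifting patient in 10 moves the before/after change by about 0.5-1.3%, but makes sulfonylurea look about 2-3% weaker against usual care.

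The fraction of recent changers, the size and speed of drift, and the AGT standard deviation are all assumed, since the documents give none of them. The dapagliflozin figure also relies on period-specific baselines; taking Visit 2 as the before value for both sequences would lose the reduction in step 2. The trial is an unpowered pilot, so the main harm is a slightly contaminated estimate carried into the planning of the definitive study.

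**What to change.** - Add to the inclusion criteria, for both arms, that all background glucose-lowering doses have been unchanged for a stated interval before the Visit 2 baseline. The sponsor sets the length.
- Require the qualifying HbA1c to have been drawn after the last change.
- Record the date of the last change at Visit 1, alongside the medication list already collected there.
- Repeat the primary analysis without any patient enrolled in breach.

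Cost: one inclusion line, one case-report field and one sensitivity analysis. A few candidates must wait before baseline, and some need a new HbA1c where an older result would have served.
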